4.8.7 Final Analysis

A final, complete analysis will be conducted after all subjects have completed the Day 361 visit; data will be monitored, cleaned, and locked before final analysis.

5 ASSESSMENT OF SAFETY

5.1 Definition of Adverse Events

The ICH Guideline for Good Clinical Practice E6(R1) defines an AE as:

Any untoward medical occurrence in a patient or clinical investigation subject administered a pharmaceutical product and which does not necessarily have a causal relationship with this treatment. An AE can therefore be any unfavorable and unintended sign (including an abnormal laboratory finding), symptom, or disease temporally associated with the use of a medicinal product, whether or not considered related to the medicinal product.

An AE includes but is not limited to any clinically significant worsening of a subject's pre-existing condition. An abnormal laboratory finding (including ECG finding) that requires medical intervention by the investigator, or a finding judged by the investigator as medically significant should be reported as an AE. If clinical sequelae are associated with a laboratory abnormality, the diagnosis or medical condition should be reported (eg, renal failure, hematuria) not the laboratory abnormality (eg, elevated creatinine, urine red blood cell [RBC] increased). Abnormal laboratory values that are not, in the investigator's opinion, medically significant and do not require intervention should not be reported as AEs.

Adverse events may be treatment emergent (ie, occurring after initial receipt of investigational product) or nontreatment emergent. A nontreatment-emergent AE is any new sign or symptom, disease, or other untoward medical event that begins after written informed consent has been obtained but before the subject has received investigational product.

Elective treatment or surgery or preplanned treatment or surgery (scheduled prior to the subject being enrolled into the study) for a documented pre-existing condition that did not worsen from baseline is not considered an AE (serious or nonserious). An untoward medical event occurring during the prescheduled elective procedure or routinely scheduled treatment should be recorded as an AE or SAE.

5.2 Definition of Serious Adverse Events

An SAE is any AE that:

- Results in death
- Is immediately life-threatening
- Requires inpatient hospitalization or prolongation of existing hospitalization
- Results in persistent or significant disability/incapacity
- Is a congenital anomaly/birth defect in offspring of the subject
- Is an important medical event that may jeopardize the subject or may require medical intervention to prevent one of the outcomes listed above

Medical or scientific judgment should be exercised in deciding whether expedited reporting is appropriate in this situation. Examples of medically important events are intensive treatment in an emergency room or at home for allergic bronchospasm, a blood dyscrasia, or convulsions that do not result in hospitalizations; or development of drug dependency or drug abuse.

5.3 Definition of Adverse Events of Special Interest

An AESI is one of scientific and medical interest specific to understanding of the investigational product and may require close monitoring and rapid communication by the investigator to the sponsor. An AESI may be serious or nonserious. The rapid reporting of AESIs allows ongoing surveillance of these events in order to characterize and understand them in association with the use of this investigational product.

Hepatic function abnormality meeting the definition of Hy's law is considered an AESI and is considered immediately reportable. See Section [5.7.2](#) for the definition and reporting of AESIs of hepatic function abnormality.

Anaphylaxis is considered an AESI and is immediately reportable. See Section [5.7.3](#) for the definition and reporting of AESIs of anaphylaxis.

Certain AEs after receipt of an adjuvanted vaccine are considered AESIs and are immediately reportable. See Section [5.7.4](#) for the definition and reporting of AESIs for an adjuvanted vaccine.

5.4 Definition of New Onset Chronic Disease

A NOCD is a newly diagnosed medical condition that is of a chronic, ongoing nature. It is observed after receiving the investigational product and is assessed by the investigator as medically significant. Examples of NOCDs include but are not limited to diabetes, asthma, autoimmune disease (eg, lupus, rheumatoid arthritis), and neurological disease (eg, epilepsy). Events that would not be considered an NOCD are mild eczema, diagnosis of a congenital anomaly present at study entry, or acute illness (eg, upper respiratory tract infection, otitis media, bronchitis).

5.5 Recording of Adverse Events, Serious Adverse Events, Adverse Events of Special Interest, and New Onset Chronic Diseases

Adverse events, including AESIs and NOCDs, will be recorded on the eCRF using a recognized medical term or diagnosis that accurately reflects the event. These events will be assessed by the investigator for severity, relationship to the investigational product, and whether the event meets criteria of an SAE and/or an immediately reportable AESI and therefore requires immediate notification of MedImmune Patient Safety. See Section [5.2](#) for the definition of SAEs, Section [5.7](#) for AESI events that require immediate reporting, [Appendix 2](#) for guidelines for assessment of severity and relationship, and [Appendix 4](#) for Tables for Clinical Abnormalities (Local Reactions, Vital Signs, Systemic [General]). If an

AE evolves into a condition that meets the regulatory definition of “serious,” it will be reported on the SAE/AESI report form.

The results of clinical laboratory tests obtained as part of this protocol (Section 4.3.3) will be transferred directly from the laboratory. Laboratory values flagged as abnormal need not be routinely entered as AEs; however, if the investigator considers that any laboratory result is clinically significant and cannot be considered to be part of an AE reported under another medical diagnosis (eg, elevated creatinine need not be reported if renal failure is reported), it should be reported as an AE.

Vital signs will not be collected on the eCRF. If the investigator considers it appropriate to report vital signs as AEs (ie, the result is clinically significant and is not included as part of an AE reported under a different medical diagnosis), the Tables for Clinical Abnormalities (Appendix 4) provide guidance for grading of these vital signs.

New onset chronic diseases will be recorded on the eCRF AE page using a recognized medical term or diagnosis that accurately reflects the event. A NOCD might also be an SAE (Section 5.2) and/or an AESI (Section 5.3); if so, it should also be reported as an SAE and/or AESI. See Section 5.6 for instructions on how to report SAEs and AESIs to MedImmune Patient Safety. A NOCD will be assessed by the investigator for relationship to the investigational product, treatments used or planned, and whether the event meets criteria of an AE, SAE, or an immediately reportable AESI.

5.5.1 Time Period for Collection of Adverse Events

Adverse events will be collected from time of signature of informed consent throughout the treatment period and including the follow-up period through Day 28 unless they meet criteria as an SAE or AESI.

All AESIs that do not meet criteria for anaphylaxis (see Section 5.7.3) will be collected from the time of dosing through Day 360.

All SAEs will be recorded from the time of informed consent through the day of last subject contact (Day 361+10, Visit 17).

All NOCDs will be recorded from the time of dosing through Day 360.

5.5.2 Follow-up of Unresolved Adverse Events

Adverse events/SAEs/AESIs should be followed until resolution or marked as ongoing at the subject’s last visit (Day 361/Visit 17). MedImmune retains the right to request additional

information for any subject with ongoing AE(s)/SAE(s)/AESI(s) at the end of the study, if judged necessary.

5.6 Reporting of Serious Adverse Events

Within 24 hours of identifying an SAE, regardless of the presumed relationship to the investigational product, the investigator or qualified designee must complete the SAE/AESI Report Form and fax it to MedImmune Patient Safety.

MedImmune contact information:

Patient Safety
MedImmune
[name]
[name]
[contact]

The sponsor is responsible for reporting certain SAEs and/or AESIs as expedited safety reports to applicable regulatory authorities, ethics committees, and participating investigators, in accordance with ICH guidelines and/or local regulatory requirements. The sponsor may be required to report certain SAEs and/or AESIs to regulatory authorities within 7 calendar days of being notified about the event; therefore, it is important that investigators submit additional information requested by the sponsor as soon as it becomes available.

Investigators should provide all available information at the time of SAE/AESI Report Form completion. Investigators should not wait to collect additional information to fully document the event before notifying MedImmune Patient Safety of an SAE and/or AESI. When additional information becomes available, investigators should submit a follow-up SAE/AESI Report Form (separate from the initial report form) with the new information. Any follow-up information to an SAE and/or AESI also needs to be provided to MedImmune Patient Safety within 24 hours of learning of the new information.

5.7 Other Events Requiring Immediate Reporting

5.7.1 Overdose

An overdose is one type of AESI and is defined as a subject receiving a dose of investigational product in excess of that specified in the Investigator's Brochure. It should be recorded in the eCRF using the term "overdose."

Any overdose of a study subject with the investigational product, with or without associated AEs/SAEs/AESIs is required to be reported within 24 hours of knowledge of the event to MedImmune Patient Safety using the Safety Fax Notification Form (see Section 5.6 for contact information). If the overdose results in an AE, the AE must also be recorded on the AE eCRF (see Section 5.5). Overdose does not automatically make an AE serious, but if the consequences of the overdose are serious, for example death or hospitalization, the event is serious and must be reported as an SAE (see Section 5.5 and Section 5.6). MedImmune does not recommend specific treatment for an overdose. The investigator will use clinical judgment to treat any overdose.

5.7.2 Hepatic Function Abnormality

Adverse events of hepatic function abnormality of special interest to the sponsor are defined as any increase in ALT or AST to greater than $3 \times$ upper limit of normal (ULN) **and concurrent** increase in bilirubin to greater than $2 \times$ ULN (ie, Hy's law cases). Concurrent findings are those that derive from a single blood draw or from separate blood draws taken within 8 days of each other. In the event of hepatic function abnormality where the etiology is unknown, timely follow-up investigations and inquiries should be initiated by the investigational site, based on medical judgment, to make an informed decision regarding the etiology of the event.

If the underlying diagnosis for the hepatic function abnormality is known, and it is not considered attributable to investigational product, the diagnosis should be recorded as an AE/SAE and is not reportable as an AESI.

If the underlying diagnosis for the hepatic function abnormality remains unknown, the term "hepatic function abnormal" should be used to report the AE/SAE, and the event is an AESI.

Hepatic function abnormality of unknown etiology, or which is considered attributable to investigational product, is required to be reported as "hepatic function abnormal" **within 24 hours of knowledge of the event** to MedImmune Patient Safety using the SAE/AESI Report Form, even if the event is considered to be nonserious (see Section 5.6 for contact information). The investigator will review the data with the medical monitor. The investigator should then use clinical judgment to establish the cause based on local standard of care and follow the subject by conducting testing as clinically indicated.

Each reported event of hepatic function abnormality will be followed by the investigator and evaluated by the sponsor.

5.7.3 Anaphylaxis

Anaphylaxis is an acute onset, potentially fatal, systemic allergic reaction that is distinct from simple allergic reactions (illness of skin or mucosa or both, such as rash, pruritus) because of the simultaneous involvement of several organ systems.

Investigators should consider the guidance provided in [Appendix 3](#) when evaluating a patient for a diagnosis of anaphylaxis. Events of anaphylaxis should be recorded as anaphylaxis. For analysis, all events that are MedDRA coded as the preferred term “anaphylaxis” will be analyzed as events of anaphylaxis.

5.7.4 Adverse Events of Special Interest for an Adjuvanted Vaccine

Adverse events of special interest for an adjuvanted vaccine include the following verbatim terms and, for analysis, will also include associated MedDRA terms. Events that are faxed in by investigators as potential AESIs for an adjuvanted vaccine that do not meet these criteria will not be analyzed as AESIs.

- Neuroinflammatory disorders:
 - Optic neuritis
 - Uveitis
 - Multiple sclerosis
 - Demyelinating disease
 - Transverse myelitis
 - Guillain-Barré syndrome
 - Myasthenia gravis
 - Encephalitis
 - ADEM (acute disseminated encephalomyelitis)
 - Neuritis
 - Bell’s Palsy
- Musculoskeletal and connective tissue disorders:
 - Rheumatoid arthritis
 - Juvenile rheumatoid arthritis
 - Polymyalgia rheumatica
 - Psoriatic arthropathy
 - Ankylosing spondylitis
 - Spondyloarthropathy
 - Systemic lupus erythematosus
 - Cutaneous lupus

- Sjogren's syndrome
- Scleroderma
- Dermatomyositis
- Polymyositis
- Mixed connective tissue disease
- Vasculitides:
 - Vasculitis
 - Temporal arteritis
 - Wegener's granulomatosis
 - Behçet's syndrome
- Gastrointestinal disorders:
 - Crohn's disease
 - Ulcerative colitis
 - Inflammatory bowel disease (non-specific)
 - Celiac disease
 - Autoimmune hepatitis
 - Primary sclerosing cholangitis
 - Primary biliary cirrhosis
- Renal disorders:
 - Glomerulonephritis
 - Nephritis
- Cardiac disorders:
 - Carditis
 - Pericarditis
 - Myocarditis
- Skin disorders:
 - Psoriasis
 - Vitiligo
 - Raynaud's phenomenon
 - Erythema nodosum
 - Autoimmune bullous skin diseases
 - Stevens-Johnson syndrome
- Hematologic disorders:
 - Autoimmune hemolytic anemia
 - Idiopathic thrombocytopenic purpura
 - Antiphospholipid syndrome
- Metabolic disorders:

- Autoimmune thyroiditis
- Grave's disease (or its synonym, Basedow's disease)
- Hashimoto's thyroiditis
- Insulin-dependent diabetes mellitus
- Addison's disease
- Other disorders:
 - Sarcoidosis

5.7.5 Reporting and Recording of Adverse Events of Special Interest

Events of overdose, hepatic function abnormality, anaphylaxis, and AESIs for an adjuvanted vaccine (as defined in Section 5.3) are required to be reported *within 24 hours of knowledge of the event* to MedImmune Patient Safety using the SAE/AESI Report Form, even if the event is considered to be nonserious (see Section 5.6 for contact information).

Adverse events of special interest also should be recorded in the eCRF according to the definitions of AE and SAE (Section 5.1 and Section 5.2).

5.8 Solicited Symptoms

Solicited symptoms are events that are considered likely to occur post dosing. For this study, solicited symptoms include:

Local reaction to investigational product injection

- Pain at the site of injection
- Tenderness or soreness at the site of the injection
- Redness at the site of the injection
- Swelling at the site of the injection

Systemic symptoms that might be related to investigational product injection

- Fever $\geq 100.4^{\circ}\text{F}$ ($\geq 38^{\circ}\text{C}$) by any route
- Headache
- Generalized muscle aches
- Fatigue or tiredness

Solicited symptoms are recorded whether or not they are treatment emergent (ie, ongoing from prior to investigational product dosing). Solicited symptoms are not necessarily

considered to be AEs but should also be recorded as AEs when, according to the judgment of the investigator, they meet the definition of an AE. The definition of fever for this study is temperature measured by any route that is $\geq 38^{\circ}\text{C}$ or $\geq 100.4^{\circ}\text{F}$ ([Marcy et al, 2004](#)).

Investigators who consider a temperature lower than this cut-off for fever or a “fever” reported by subjects without documentation by thermometer to represent an AE should record the event as “elevated body temperature.” Because solicited symptoms are events that might be expected to occur after immunization, they will not be assessed for relationship to investigational product. They will not be MedDRA coded. They will be assessed for severity by the investigator consistent with the Tables for Clinical Abnormalities (Local Reactions, Vital Signs, Systemic [General]) provided in [Appendix 4](#) and the diary card.

The reporting period for solicited symptoms for subjects receiving a single dose is 7 days after vaccination/investigational product administration.

Solicited symptoms will be reported using the terms as defined in this protocol. Diary cards will be provided for subjects to record solicited symptoms during Days 1 through 7. Thermometers and measuring tapes will also be provided for subject assessment of local reactions. The investigator must collect the diary cards to serve as source documentation. Solicited symptoms should be recorded in the eCRF. Investigators or their designees should question the subjects about solicited symptoms to confirm assessment of severity. If, upon questioning, a subject provides updated solicited symptom information that either changes or supplements that recorded on the diary card, the investigator or designee should record the updated data in the eCRF for the solicited symptom(s) and must note on the diary card that the data have been updated by the subject. This note must be signed and dated by site staff but subject signatures are not required. If, in the judgment of the investigator, a solicited symptom also warrants reporting as an AE or SAE, it should be recorded as stated in [Section 5.5](#).

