2.2 Study Endpoints

2.2.1 Primary Endpoint

The primary endpoint is the safety and tolerability of single ascending doses of RSV sF and MEDI7510 as assessed by the occurrence of all solicited symptoms (whether or not treatment emergent) and treatment-emergent adverse events (AEs), serious adverse events (SAEs), new onset chronic diseases (NOCDs), and adverse events of special interest (AESIs) as follows:

- The proportion of subjects experiencing each solicited symptom from administration of investigational product (Day 1) through Day 7 post vaccination (7 days)
- The proportion of subjects experiencing each AE from administration of investigational product (Day 1) through Day 28 post vaccination (28 days)
- The proportion of subjects experiencing each SAE from administration of investigational product (Day 1) through Day 28 post vaccination (28 days)

- The proportion of subjects experiencing each SAE from administration of investigational product (Day 1) through Day 360 post vaccination (360 days)
- The proportion of subjects experiencing each NOCD from administration of investigational product (Day 1) through Day 360 post vaccination (360 days)
- The proportion of subjects experiencing each AESI from administration of investigational product (Day 1) through Day 360 post vaccination (360 days)

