3.2.2 Rationale for Study Population

The subject population selected for this FTIH study is that of older adults, a group that will be the target of efficacy studies of this vaccine because older adults are at greater risk of medically significant RSV disease than younger adults. Older adults also have been shown to have an immune response to RSV that differs from that of younger adults in that, while their antibody levels are similar to those of younger individuals, they have lower cell-mediated immune responses ([Cherukuri et al, 2013](#)).

A population of older adults that is generally healthy or that has stable, chronic underlying medical conditions was selected for this FTIH study, because enrolling adults ≥ 60 years of age who are completely healthy did not appear feasible and, in addition, would skew the enrollment population towards those closer to 60 years of age. Subjects with any history of autoimmune disorder will be excluded from this FTIH study because some subjects will receive adjuvant. Immunosuppressed subjects will also be excluded because they would be expected to have altered immune responses to vaccines. Finally, in the absence of any data on local site reactions, subjects with a history of thrombocytopenia or bleeding disorder will be excluded from this FTIH protocol. These older adults are an acceptable study population for this FTIH study from a safety perspective, and a preferred study population from an immunological perspective, because they represent the target population for the MEDI7510 vaccine. Younger adults do not have deficient cell-mediated immune responses and thus would not provide data for dose selection in older adults ([Cherukuri et al, 2013](#)). Older adults with more complicated medical problems, although ultimately planned for inclusion in future studies, will not be included in this FTIH study both to enhance the safety of the subjects and to provide a clearer assessment of vaccine safety.

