16. Receipt of any investigational product in the 90 days prior to randomization or expected receipt of investigational product during the period of study follow-up
17. Receipt of immunoglobulins or blood products within 4 months of study dosing (120 days) or expected receipt of investigational product during the period of study follow-up
18. History of thrombocytopenia or bleeding disorder or use of anticoagulants such as warfarin, heparin/low molecular weight heparin, thrombin inhibitors (dabigatran and others), or factor Xa inhibitors (rivaroxaban, apixaban, and others). Subjects receiving drugs with anti-platelet activity such as nonsteroidal antiinflammatory drugs, clopidogrel or aspirin are not excluded.

19. Expected receipt of antipyretic or analgesic medication on a daily or every other day basis from randomization through 72 hours after receipt of investigational product (Note: A daily dose of ≤ 163 mg of aspirin is not considered a contraindication to enrollment.)
20. Subjects who have significant scarring, tattoos, abrasions, cuts, or infections over the deltoid region of both arms that, in the opinion of the investigator, could interfere with evaluation of injection site local reactions.
21. Any condition that, in the opinion of the investigator, would interfere with evaluation of the investigational product or interpretation of subject safety or study results
22. Concurrent enrollment in another clinical study that involves any invasive clinical procedure, including phlebotomy.
23. History of alcohol or drug abuse or psychiatric disorder that, in the opinion of the investigator, would affect the subject's safety or compliance with study
24. Employees of individuals directly involved with the conduct of the study, individuals who themselves are involved with the conduct of the study, or immediate family members of such individuals

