4.2.2.1 Description of Study Procedures, Treatment Period

Day 1: Dosing (Visit, V2)

1. Update medical history, including concomitant medications
2. Perform physical examination to update since screening, including weight
3. Collect vital signs
4. Verify eligibility criteria
5. Randomize and assign product kit number
6. Collect urine for urinalysis (may be collected after phlebotomy)
7. Collect blood samples (see Laboratory Manual for details):
 - for serum chemistry and hematology
 - for potential use in assessing treatment-emergent safety events
 - for humoral immunogenicity assays
 - for cell-mediated immunogenicity assays
8. Administer investigational product and observe for at least 30 minutes. Vital signs must be repeated between 20 and 30 minutes post dose.
9. Provide thermometers, diary cards, tape measures, and instructions for completing diary cards; ensure subject understands how to measure local reactions and take temperature
10. Assess for all solicited symptoms, and treatment-emergent AEs, SAEs, NOCDs, and AESIs
11. Record all concomitant medications

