4.8.3 Safety

The primary endpoint is the safety and tolerability of RSV sF and MEDI7510 as assessed by the occurrence of all solicited symptoms (whether or not treatment emergent) and treatment-emergent AEs, SAEs, NOCDs, and AESIs.

Safety evaluations will be descriptive in nature, and observed differences will be evaluated for medical relevance.

Solicited symptoms, whether or not treatment emergent, will be summarized by day and overall, and by severity. They will not be coded using the Medical Dictionary for Regulatory Activities (MedDRA) and will be summarized regardless of whether or not they are treatment emergent. They will not be assessed by relationship to investigational product, because they are assumed to be possibly related. Treatment-emergent AEs, SAEs, NOCDs, and AESIs will be summarized by system organ class and preferred term using MedDRA. Adverse events, SAEs, and AESIs will also be summarized by severity and relationship to investigational product, and NOCDs will be summarized by relationship.

Summaries of solicited symptoms through Day 7 post dose, AEs and SAEs through Day 28 post dose, and SAEs, NOCDs, and AESIs through Day 360 post dose will be provided.

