- An unreasonable temporal relationship between administration of the investigational product and the onset of the event (eg, the event occurred either before, or too long after, administration of the investigational product for it to be considered product-related)
- A causal relationship between the investigational product and the event is biologically implausible (eg, death as a passenger in an automobile accident)
- A clearly more likely alternative explanation for the event is present (eg, typical adverse reaction to a concomitant drug and/or typical disease-related event)

Individual AE/SAE reports will be considered “related” to use of the investigational product if the “not related” criteria are not met.

“Related” implies that the event is considered to be “associated with the use of the drug” meaning that there is “a reasonable possibility” that the event may have been caused by the product under investigation (ie, there are facts, evidence, or arguments to suggest possible causation).

Relationship to Protocol Procedures

The investigator is also required to provide an assessment of relationship of SAEs to protocol procedures on the SAE/AESI Report Form. This includes nontreatment-emergent SAEs (ie, SAEs that occur prior to the administration of investigational product) as well as treatment-emergent SAEs. A protocol-related SAE may occur as a result of a procedure or intervention required during the study (eg, blood collection). The following guidelines should be used by investigators to assess the relationship of SAEs to the protocol:

Protocol related: The event occurred due to a procedure/intervention that was described in the protocol for which there is no alternative etiology present in the subject’s medical record.

Not protocol related: The event is related to an etiology other than the procedure/
intervention that was described in the protocol (the alternative etiology must be documented
in the study subject's medical record).

Appendix 3 National Institute of Allergy and Infectious Diseases and Food Allergy and Anaphylaxis Network Guidance for Anaphylaxis Diagnosis

The National Institute of Allergy and Infectious Diseases and the Food Allergy and Anaphylaxis Network define anaphylaxis as a serious allergic reaction that is rapid in onset and may cause death ([Sampson et al, 2006](#)).

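### The solicited-symptom endpoint counts symptoms present before the injection and no pre-dose score is scheduled, so new or worsened headache, muscle aches and fatigue cannot be reliably separated from unchanged ones

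*Protocol*

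**What the plan says.** Section 2.2.1 defines the primary endpoint through the "occurrence of all solicited symptoms (whether or not treatment emergent"), and its first component is "The proportion of subjects experiencing each solicited symptom from administration of investigational product (Day 1) through Day 7 post vaccination (7 days"). The synopsis and Section 4.8.3 repeat the rule.

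Section 5.8 applies it to recording: "Solicited symptoms are recorded whether or not they are treatment emergent (ie, ongoing from prior to investigational product dosing"). The parenthesis is loosely placed, since it describes symptoms that are not treatment emergent, but the intent is clear. Section 5.8 lists four local symptoms and four systemic ones: fever, headache, generalized muscle aches, and fatigue or tiredness.

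On causality, Section 4.8.3 says: "They will not be assessed by relationship to investigational product, because they are assumed to be possibly related". The symptoms are summarised by day, overall and by severity, and differences between arms are judged descriptively for medical relevance.

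The Day 1 procedures in Section 4.2.2.1 put the injection at step 8, the handing out of the diary at step 9, and the symptom assessment at step 10: "Assess for all solicited symptoms, and treatment-emergent AEs, SAEs, NOCDs, and AESIs". Steps 1 and 2 update the history and examination before dosing. No step before the injection records the solicited symptoms or grades them.

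**The concern.** Section 3.2.2 describes who is enrolled: "A population of older adults that is generally healthy or that has stable, chronic underlying medical conditions was selected for this FTIH study". In adults of 60 or older, headache, muscle aches and fatigue can be long-standing. Under Appendix 4 (Table 9-3), Grade 1 for each of these needs only that activity is not affected. A subject with unchanged mild fatigue can therefore count as a solicited-fatigue case whichever injection is given.

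If the background is common, the reported systemic rates mix it with vaccine effect. These rates form part of the safety data at the interim analysis from which the Phase 1b antigen dose is chosen (Section 4.8.6). A graded pre-dose score cannot be reliably rebuilt once the subject has been injected, so a later analysis plan could not fully repair the gap.

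**Working it through.** **Inputs from the protocol.** There are six cohorts of 20 active and 4 placebo subjects (Table 3.1.2-1), so 6 × 24 = 144 as stated. Placebo recipients are pooled (Section 4.8.1), giving 6 × 4 = 24. The protocol states no solicited-symptom rate, effect size or power, so it has no figure of its own to reproduce on this point.

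**Assumed inputs.** Let b be the proportion of subjects with a given systemic symptom before dosing, and v the proportion in whom the vaccine causes it. The protocol gives neither. I take v = 15% and b = 10%, 20% and 30%. The model treats the two as independent, ignores new background symptoms that arise in Days 1 to 7, and lets a subject count once.

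**Rates and difference.** Active rate = b + (1 - b)v. Placebo rate = b. Difference = (1 - b)v.

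| b | Active | Placebo | Difference |
|---|---|---|---|
| 0% | 15% | 0% | 15 points |
| 10% | 0.10 + 0.90 × 0.15 = 23.5% | 10% | 13.5 points |
| 20% | 0.20 + 0.80 × 0.15 = 32% | 20% | 12 points |
| 30% | 0.30 + 0.70 × 0.15 = 40.5% | 30% | 10.5 points |

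With v = 0 the difference is zero at every b.

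**Background count per cohort.** The expected number of pre-existing cases among 20 is 20 × b, that is 2, 4 or 6. At b = 20% the binomial 2.5th to 97.5th percentile range is 1 to 8: P(X = 0) = 0.012, P(X ≤ 7) = 0.968, P(X ≤ 8) = 0.990.

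**Noise between two dose cohorts of 20 with the same true rate p.** Standard error = √(2p(1 - p)/20).
- No background, p = 0.15: √(0.1 × 0.15 × 0.85) = 11.3 points.
- b = 10%, p = 0.235: √(0.1 × 0.235 × 0.765) = 13.4 points.
- b = 20%, p = 0.32: √(0.1 × 0.32 × 0.68) = 14.8 points.
- b = 30%, p = 0.405: √(0.1 × 0.405 × 0.595) = 15.5 points.

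**Chance gaps from background alone (v = 0), exact binomial sums.** The probability of a gap of 20 points or more in either direction at b = 10%, 20% and 30% is:
- two cohorts of 20: 6.3%, 16.4% and 22.6%;
- a cohort of 20 against the pooled 24: 4.2%, 10.1% and 15.6% (0.8% at b = 5%).

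**The case against.** The best defence is that this is a deliberate all-inclusive rule for a first-in-human safety study. It avoids case-by-case attribution and is the same in the synopsis and in Sections 2.2.1, 4.8.3 and 5.8. Saline recipients are randomised, blinded and counted in the same way, so the control arm measures the background. This stands, and it is why the all-symptom count should stay.

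A reader might infer that the rule contradicts Appendix 2, which treats an event as unrelated if, for example, "the event occurred either before, or too long after, administration of the investigational product for it to be considered product-related". It does not. Appendix 2 governs AEs and SAEs, and Section 5.8 says solicited symptoms are not necessarily AEs and exempts them from relationship assessment. One that the investigator judges to be an AE is recorded as such as well, and then falls under Appendix 2.

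A reader might also infer that chronic symptoms are reported as caused by the vaccine. The documents do not support that either: what is interpreted is the difference between arms, and its expectation is zero when the vaccine does nothing.

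The scope is narrow. Injection-site reactions rarely pre-exist, and fever or acute illness on or just before the randomisation day excludes a subject. Near-daily analgesic use is also an exclusion if expected "on a daily or every other day basis from randomization through 72 hours" after dosing, which limits chronic pain but not fatigue or untreated aches. Stopping criterion 5 uses related AEs, not raw symptom counts.

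Two further points stand in part. The history update and the severity tables give some information on background and worsening, and the diary and eCRF are not shown, so any onset fields are unknown. But neither the history update nor the severity tables supply a graded pre-dose score for each symptom. The dilution is also small against sampling error. At b = 20% it is 15 - 12 = 3 points, while the standard error of 32% in 20 against 20% in 24 is √(0.32 × 0.68/20 + 0.20 × 0.80/24) = 13.2 points.

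**Conclusion.** The point holds as an interpretive weakness, not an error or a contradiction. Pre-existing symptoms enter the primary endpoint, and the Day 1 procedures contain nothing that reliably separates them from new or worsened ones. In practice this concerns three of the eight solicited symptoms: headache, generalized muscle aches and fatigue.

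Three effects remain: higher absolute rates in every arm, a true difference multiplied by (1 - b), and more noise between cohorts. The last matters most for dose selection. The protocol describes randomisation only within cohorts, and these largely enrol in sequence (Section 3.1.3), so balance of chronic symptoms across doses is not assured by design. All sizes rest on assumed b and v. If b is near 5%, the loss on a 15-point effect is 0.05 × 15 = 0.75 points. Severity is low, and the reason to act is that the remedy is cheap and the baseline must be taken before dosing.

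**What to change.** In Section 4.2.2.1 and Table 4.2.2-1, add to Day 1, before the injection, a record of the presence and grade of the systemic solicited symptoms, on the Appendix 4 scale. In Section 4.8.3, keep the all-symptom summary as the endpoint. Beside it, add a summary by arm of solicited symptoms that are new or worsened in grade after dosing. Replacing the endpoint with that summary would be a debatable trade-off and is not needed.

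The cost is a few questions at a visit that already takes a history and examination, one eCRF page and one extra table. The added table will not remove background symptoms that happen to begin after dosing; the placebo arm still has to account for those.
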